Power analysis was performed to estimate an adequate sample size to support statistical conclusion validity and so that correct inferences can be made about the relationships between study variables. The standardized effect size was calculated to equal 0.5. Assuming an alpha of 0.05, power of 0.80 and a standardized effect size of 0.5, 64 patients will be required for each treatment group based on anticipated difference in patient reported pain scores due to sciatic PNB technique. Projected sample sizes were increased approximately ten percent from 64 per group to total of 70 subjects per group in an effort to account for patient attrition and lost data, therefore, a total of 140 patients will be enrolled in the study. Additionally, if the loss in patients is unequal between groups, yielding a significant disparity between study group composition, additional subjects may be added to account for this unequal loss.

Despite the presence of multiple confounding variables, the calculated sample size is sufficient to determine if a significant difference in outcomes measures exists secondary to sciatic PNB technique. Additionally, the sample size does not need to be altered based on the equation: $N > 50 + 8k$, where N is the number of cases and k is the number of predictors (Warner, 2013). In this study there is only one predictor, sciatic PNB technique, which is anticipated to impact outcomes following ACL reconstruction.

E. Randomization:

A computer generated randomization scheme will be used to assign 70 patients to each treatment group. The randomization will be done using the maximum allowable percent deviation method. This algorithm conducts a search to find a randomization list for which all percent deviations are less than or equal to the maximum allowable percent deviation of 10%. The randomization scheme will be sent to the PI who will then prepare and maintain a log of subject assignments. The PI will notify the participating surgeon and anesthesia team of the treatment (single-injection or continuous sciatic PNB) that is to be given to the next consented patient. The research coordinator will remain blinded to the assigned treatment plan until data collection has been completed.

F. Components of Cincinnati Children's Hospital Medical Center to be Utilized for this Study:

Subjects undergoing unilateral ACL reconstruction with a hamstring autograft on an outpatient basis at the Liberty Campus of CCHMC will be recruited from the OR schedule.

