G: Data Collection:

Participants will be in the research study for approximately 4 days; the day of surgery and for follow-up phone calls once a day for the first three days after surgery. A minimum of three phone calls may be made after the patient is discharged. Once enrolled in the study, a unique study identification number will be assigned to each study participant. Assigning a unique patient identifier to each study participant allows any data gathered pertaining to them to be attached to this number rather than any patient identifiers, further ensuring that a breach in confidentiality does not occur (Polit & Beck, 2012). After obtaining written consent from the guardian(s), the medical record of the patient will be reviewed for further inclusion and exclusion criteria.

All data gathered will be used specifically for research purposes. Data collected preoperatively will include age, gender, BMI, ASA physical status, previous surgical history, self-reported tolerance of pain, self-reported level of activity since time of ACL injury, and the name of the orthopedic surgeon scheduled to perform ACL reconstruction. In addition, several questions regarding the patient's anxiety level will be asked to determine whether or not the patient has a history of anxiety that may impact pain and/or satisfaction scores postoperatively (see Appendix A). This data will be collected from the patient's medical record during the preoperative phase and directly from the patient and/or guardian(s) when appropriate. Data on study group assignment, analgesic requirement, the length of surgery, length of pneumatic tourniquet inflation time, pneumatic tourniquet inflation pressure, and systolic blood pressure at time of pneumatic tourniquet inflation will be gathered during the intraoperative phase.

In an effort to discern the impact of sciatic PNB technique on the outcome measures, data on self-reported pain scores, doses of oral pain medications, unplanned admission to the hospital due to poor pain control, and patient satisfaction will be gathered while the patient remains in the post anesthesia care unit (PACU). Data collection will then continue for 72 hours postoperatively following discharge from the PACU. Patients will document data measures on supplied data collection instruments (see Appendix B).

The patient or their guardian will record pain scores once every 6 hours for 72 hours postoperatively. In addition, the patient or their guardian will note the

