The hypothesis that the extended duration of analgesia offered by continuous sciatic PNB decreases pain scores during the initial 72 hours following hamstring autograft harvest when compared to single-injection sciatic PNB will be tested with two separate tests. Both Pearson's correlation and the Wilcoxon Mann Whitney test will be utilized to test his hypothesis, as controversy surrounds the analysis of Likert scale data. It has been argued that only nonparametric statistics should be used on Likert scale data, as the intervals between the scale values may not be equal (Jamison, 2004). Taking this into consideration, the pain scores recorded for each patient will be totaled and an average pain score will be calculated for each study participant. This will allow the data to be measured on a continuous scale, thereby meeting the criteria of Pearson's correlation. Pearson's correlation is a parametric test that measures the degree and direction of linear relationship between two variables (Gravetter & Wallnau, 2000). The Wilcoxon Mann Whitney test will also be used to analyze pain scores recorded at each 12-hour period to determine if there is a difference in outcomes related to the duration of analgesia provided by sciatic PNB technique. This test is appropriate when there is one IV with two independent groups and the DV is ordinal in nature. The Wilcoxon Mann Whitney test is a nonparametric test of the null hypothesis that two populations are the same against an alternative hypothesis. This test uses the relative position of the data in a rank ordering, rather than the actual values. Using both parametric and nonparametric tests will increase confidence when drawing conclusions should both tests lead to the same results.

The hypothesis that the extended duration of analgesia offered by continuous sciatic PNB decreases oral pain medication use during the initial 72 hours following hamstring autograft harvest when compared to single-injection sciatic PNB will be tested with the Independent Samples *t*-Test. The Independent Samples *t*-Test is appropriate when there is one IV with two independent groups and the DV is continuous in nature (Field, 2009). The Independent Samples *t*-Test is used to compare differences between separate groups when there are two experimental groups (single-injection sciatic PNB and continuous sciatic PNB) and different study participants have been used in each group (Field, 2009).

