The hypothesis that the extended duration of analgesia offered by continuous sciatic PNB decreases the incidence of unplanned admission due to poor pain control during the initial 72 hours following hamstring autograft harvest when compared to single-injection sciatic PNB will be tested with the Chi-square test. The Chi-square test is used to determine if there is a relationship between two categorical variables (Field, 2009). As the data for this DV are categorical, the focus during analysis is placed on frequencies rather than means. The Chi-square test can be used to determine if there is a significant difference between the expected frequencies and observed frequencies in one or more categories (Field, 2009).

The hypothesis that the extended duration of analgesia offered by continuous sciatic PNB does not delay active knee flexion during the initial 72 hours following hamstring autograft harvest when compared to single-injection sciatic PNB will be tested using the Wilcoxon Mann Whitney test. The hypothesis that the extended duration of analgesia offered by continuous sciatic PNB improves patient satisfaction during the initial 72 hours following hamstring autograft harvest when compared to single-injection sciatic PNB will also be tested using the Wilcoxon Mann Whitney test. The Wilcoxon Mann Whitney test is appropriate to test both these hypotheses, as this test is designed to evaluate the difference between two treatments (single-injection sciatic PNB and continuous sciatic PNB) using data from an independent measures study (Gravetter & Wallnau, 2000). During analyses, testing may be altered based on the recommendations of the statistician to better analyze the collected data. Intention-to-treat analysis will not be employed, as this may skew results and it is often difficult to obtain outcome data for study participants who have dropped out of the study (Polit & Beck, 2012).

Prior to any analyses, the distribution of the demographic variables will be compared between the two treatment groups. All statistical tests will be two-sided with a significance level of $\alpha=0.05$ and will be conducted using SAS[®] software, (Version 9.2, Cary, NC). Following the enrollment of the initial 30 subjects (with 15 in each study group), an interim analysis utilizing the statistical tests later described will be performed to determine if statistically

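### The 72-hour pain average takes no account of which of the 12 scheduled scores are present, so early-stopped diaries dilute a 24–48 h effect and could bias the comparison if stopping differs by arm

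*Combined protocol and SAP*

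**What the plan says.** Section V.G states that the patient or guardian "will record pain scores once every 6 hours for 72 hours postoperatively", and Appendix B has a box for each of the 12 times from 6 to 72 hours. Section VI.B then reduces the diary to one number per patient: "the pain scores recorded for each patient will be totaled and an average pain score will be calculated". That number goes into Pearson's correlation, one of two tests of hypothesis H1.a. The other is a Wilcoxon Mann Whitney test on scores at each 12-hour period.

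The plan does not say what the total is divided by, how many entries are needed, or how a missing entry is treated. Section V.G also collects pain scores in the PACU, and VI.B does not say whether these enter the average.

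The plan expects incomplete data. Section V.D allows for attrition and lost data by enrolling more: "Projected sample sizes were increased approximately ten percent from 64 per group to total of 70 subjects per group". Section VI.B declines intention-to-treat, partly because "it is often difficult to obtain outcome data for study participants who have dropped out".

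**The concern.** An average of recorded scores is comparable between patients only if the scores cover the same hours, or if pain and the treatment contrast are flat over time. The plan's own rationale says that the contrast is not flat. Section I puts the single injection at up to 24 hours, section V.A stops the sciatic infusion at 48 hours, and scoring runs to 72 hours. The arms should therefore separate mainly between about 24 and 48 hours.

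A patient who stops recording at 24 hours contributes an average that contains none of that window, with the same weight as a full 12-score average. Two things are at stake:

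- **Dilution.** The estimated 72-hour difference shrinks and power falls, even if stopping is equal in the two arms.
- **Bias.** If stopping differs by arm, the averages can differ without any treatment effect. This is possible because section V.A leaves patients unblinded.

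Enrolling extra patients makes up lost numbers. It corrects neither problem.

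**Working it through.** **1. The plan's own figure.** Section V.D: "Assuming an alpha of 0.05, power of 0.80 and a standardized effect size of 0.5, 64 patients will be required for each treatment group"; section VI.B makes the tests two-sided. n = 2(1.960 + 0.842)² / 0.5² = 62.8, so 63 per group by the normal approximation. The exact t-test gives 63.77, so 64, with power 0.801. Inflation: 64 × 1.10 = 70.4, so 70. The sample size reproduces and does not depend on this point. An allowance of 6 in 70 is 8.6% loss per arm.

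**2. The test.** With arm as the second variable, Pearson's correlation on the averages is the same test as the pooled two-sample t-test, so the t-test is used below.

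**3. One patient, different diaries.** Assumed scores at 6, 12, …, 72 h: 2, 2, 3, 5, 6, 6, 5, 5, 5, 4, 4, 3.

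| Entries present | Average |
|---|---|
| all 12 | 50/12 = 4.17 |
| first 24 h only | 12/4 = 3.00 |
| up to 48 h | 34/8 = 4.25 |
| 24–48 h missing | 28/8 = 3.50 |
| last 24 h only | 16/4 = 4.00 |

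**4. Dilution with equal stopping.** Assumed: 70 per arm, SD 2, within-patient correlation 0.5, and an effect of −1.8 at 30, 36, 42 and 48 h only.

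- Full diaries: difference = −1.8 × 4/12 = −0.60. Variance of a 12-score mean = 4(1 + 11 × 0.5)/12 = 2.17; SE = √(2 × 2.17/70) = 0.249; 0.60/0.249 = 2.41; power ≈ Φ(2.41 − 1.96) = 67%. Simulation gives 66%.
- 10% of each arm stops after 24 h: their expected difference is 0, so the estimate is 0.9 × −0.60 = −0.54. Variance of a 4-score mean = 4(1 + 3 × 0.5)/4 = 2.5; mixed variance ≥ 0.9 × 2.17 + 0.1 × 2.5 = 2.20; SE ≥ 0.251; power ≤ Φ(0.54/0.251 − 1.96) ≈ 58%. Simulation gives 57%.
- A time-adjusted analysis of the same simulated data keeps about −0.60 and 67%.

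**5. Bias with unequal stopping and no true effect.** Bias = (difference in stopping proportions) × (early mean − full mean).

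- Curve from step 3: 0.20 × (3.00 − 4.17) = −0.23 at 30% v 10%, and 0.30 × −1.17 = −0.35 at 40% v 10%. Simulated with 64 per arm, between-patient SD 1.6 and within-patient SD 1.5, rejection rates are 11.4% and 19.5% at nominal 5%. The time-adjusted mean gives 5.6% and 4.6%.
- Flatter curves (2 rising to 5, falling to 2.5; 70 per arm, SD 2, correlation 0.5): across three such curves, type I error is 5.1–6.2% at 5% v 15% stopping and 5.4–9.4% at 5% v 25%.

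**6. Cases with little or no harm.** With no true effect, equal stopping keeps type I error at about 5%. With 10% of entries missing at random in both arms, bias is about 0.005 and rejections 5.3%; under an assumed effect, power stays at 76%.

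**The case against.** There is a fair case on the other side.

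- **The rule is partly inferred.** The text does not say that a diary abandoned at 24 h enters the test, or that the divisor is the number recorded. The rejection of intention-to-treat and the allowance for losses could mean that dropouts are left out. If early stoppers are excluded and stopping is unrelated to pain, the mechanism disappears (4.5–5.1% rejections in simulation). This stands: the inclusion of partial diaries is the natural reading, not a stated one. Dividing by 12 instead would count missing scores as zero, which is worse.
- **The large figures need large gaps.** A 20-point gap in stopping, all of it at 24 h, is a strong assumption. At about the loss that the plan allows for (5% v 15%), type I error is close to nominal. This also stands.
- **Missing entries are being limited.** There are daily calls, two training sessions, a piloted form, replacement sheets, and a gift card mailed once data collection is complete. These should help, but none says how to analyse what is still missing.
- **There is a second test.** The 12-hourly Wilcoxon tests do not mix early and late hours. They give no single 72-hour result, however, and the plan takes added confidence from agreement between the two tests, so a distorted average still matters. Leave for the statistician to alter the tests later is not a prespecified rule.

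A reader might infer that the average will show a difference that is not there. The documents do not support that: they report no stopping rate, and false positives rise only if stopping clusters in time and differs by arm.

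**Conclusion.** The concern holds as a weakness in the method, not as a demonstrated bias. The 72-hour average ignores the timing of the scores in a trial whose contrast changes with time by design, and nothing elsewhere in the plan repairs it.

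Dilution is the firmer part, because it needs no imbalance between arms: about 66% to 57% power with 10% stopping after 24 h in each arm, if the effect is confined to 24–48 h. The inflation of type I error is conditional: about 5–6% at 5% v 15% and about 5–9% at 5% v 25%, higher only with a steeper curve and wider gaps, and essentially none for equal stopping or entries missing evenly at random.

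All of these figures rest on assumed curves, SDs, correlations and stopping rates, because the documents give none; the effect size is stated only as 0.5 in standardized form. Nor should a reader conclude that the sample size is wrong: 64 and 70 per group reproduce. This is an inexpensive improvement that should be made before the data are analysed.

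**What to change.** For the 72-hour result, replace Pearson's correlation on the raw average with a repeated-measures mixed model on the 12 scheduled diary scores, with arm, time, arm-by-time and within-patient correlation. Include every randomized patient with at least one score. Report the arm difference averaged with equal weight over the 12 times. State that PACU scores are not part of this average.

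Alongside it:

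- keep the simple average as a sensitivity analysis, with its denominator stated;
- tabulate missing entries by arm and time point;
- add a sensitivity analysis for stopping related to unrecorded pain, which the mixed model does not correct.

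The cost is a paragraph of analysis-plan wording and one standard SAS procedure, with no new data and no change in sample size. The downside is a slightly more complex primary model that relies on a missing-at-random assumption.

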The purpose of this research is to compare the effect of single-injection sciatic PNB to continuous sciatic PNB on 1) postoperative pain control as measured by self-reported pain scores, pain medication use, and unplanned hospital admission due to poor pain control, 2) active knee flexion, and 3) patient satisfaction with pain control following ACL reconstruction with a hamstring autograft. The results of this research have the potential to positively impact pain control for the adolescent population undergoing this surgical procedure and foster responsible utilization of limited resources.

SPECIFIC AIM 1. The first aim of the study is to explore the impact of sciatic PNB technique on hamstring donor site pain control postoperatively.

H1.a. The extended duration of analgesia offered by continuous sciatic PNB decreases pain scores during the initial 72 hours following hamstring autograft harvest when compared to single-injection sciatic PNB.

H1.b. The extended duration of analgesia offered by continuous sciatic PNB decreases oral pain medication use during the initial 72 hours following hamstring autograft harvest when compared to single-injection sciatic PNB.

H1.c. The extended duration of analgesia offered by continuous sciatic PNB decreases the incidence of unplanned admission due to poor pain control during the initial 72 hours following hamstring autograft harvest when compared to single-injection sciatic PNB.

SPECIFIC AIM 2. The second aim of the study is to explore the impact of sciatic PNB technique on active knee flexion postoperatively.

H2. The extended duration of analgesia offered by continuous sciatic PNB does not delay active knee flexion during the initial 72 hours following hamstring autograft harvest when compared to single-injection sciatic PNB.

SPECIFIC AIM 3. The third aim of the study is to explore the impact of sciatic PNB technique on patient satisfaction with postoperative pain control.

H3.1. The extended duration of analgesia offered by continuous sciatic PNB improves patient satisfaction during the initial 72 hours following hamstring autograft harvest when compared to single-injection sciatic PNB.

IV. PREVIOUS CLINICAL EXPERIENCE

Concurrent Research Studies: The Department of Anesthesiology is not currently conducting another protocol with this patient population.

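### The pain hypothesis that sets the sample size (H1.a) has seven tests, each at 0.05, none named as decisive, and the plan lets tests be changed during analysis

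*Combined protocol and SAP*

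**What the plan says.** H1.a (section III, Specific Aim 1) states: "The extended duration of analgesia offered by continuous sciatic PNB decreases pain scores during the initial 72 hours following hamstring autograft harvest", compared with the single injection. It is the first hypothesis under VI.B, Primary Endpoint Analysis, and pain scores are the outcome on which V.D bases the sample size.

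VI.B gives the analysis: "Both Pearson's correlation and the Wilcoxon Mann Whitney test will be utilized to test his hypothesis". For the Pearson part, "the pain scores recorded for each patient will be totaled and an average pain score will be calculated for each study participant". For the other part, "The Wilcoxon Mann Whitney test will also be used to analyze pain scores recorded at each 12-hour period". The only sentence linking the two is: "Using both parametric and nonparametric tests will increase confidence when drawing conclusions should both tests lead to the same results".

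Later in VI.B every test is set at two-sided 0.05. The same section adds: "During analyses, testing may be altered based on the recommendations of the statistician to better analyze the collected data". It gives no time limit for such changes and no condition about being blind to arm. An interim analysis after 30 subjects uses the planned tests and can stop the study.

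On collection, V.G says: "The patient or their guardian will record pain scores once every 6 hours for 72 hours postoperatively". The Appendix B diary has the matching twelve boxes.

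**The concern.** Nothing says which result answers H1.a. The stated reason for two methods is to check a parametric test against a rank test, but the two are applied to different quantities: the 72-hour mean and the single 12-hour periods. They could differ for clinical reasons alone. The Background says a single injection can last up to 24 hours, and V.A runs the sciatic infusion for 48, so the arms may be alike early and differ later. Disagreement is foreseeable and the plan has no answer to it.

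With seven results at full alpha and permission to change tests during analysis, a reader of the final report could not tell a confirmed primary result from the most favourable of seven. The same tests feed the interim stopping decision, so the gap reaches the conduct of the trial as well as its reporting.

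**Working it through.** **The plan's sample size.** Inputs from V.D: alpha 0.05, power 0.80, standardized effect 0.5. Normal approximation: n = 2(1.960 + 0.842)² / 0.5² = 62.8, so 63. The exact two-sample t calculation gives 63.77, so 64 per group. The plan's figure is reproduced, for one two-sided, two-group comparison at full alpha.

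**The Pearson test is that comparison.** With arm coded 0/1, t = r√(N − 2) / √(1 − r²) is the pooled two-sample t statistic. A numerical check with 64 per group gave the same p-value for both (0.00132). Taken alone, this test holds 5%: simulated error was 4.7% to 5.2%. It does not itself give a difference in pain points.

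**Number of tests.** 72 h / 12 h = 6 Wilcoxon tests, plus 1 Pearson, is 7.

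**Chance of at least one false positive among the seven.** The reference under independence is 1 − 0.95⁷ = 30.2%. The tests are correlated, so the real figure is lower. The documents give no within-patient correlation, so 0.3 to 0.9 is assumed, equal between all times. Test statistics were simulated for the mean of twelve scores and for six periods, counting any result beyond ±1.96. The interim column comes from simulated 0–10 scores (64 per group, 15 per group at the interim, one score per period) and counts any significant result at either look.

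| Assumed correlation | One score per period | Average of two scores per period | One score, with interim look |
|---|---|---|---|
| 0.3 | 25% | 22% | 42% |
| 0.5 | 21% | 17% | 35% |
| 0.7 | 16–17% | 13% | 29% |
| 0.9 | 11% | 9% | 21% |

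The simulation of 0–10 scores gave 25%, 21%, 18% and 12% for the one-score column. With correlation that decays over time (6-hour autocorrelation 0.7 or 0.9), it gave 24% and 18%.

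**A stricter rule for comparison.** Suppose the mean-score test must be significant and at least one period must support it. Over the same correlations the error rate is about 4% to 5%, and power at 64 per group (effect 0.5 on the mean, uniform over time) is 76% to 81%.

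**Adjusting instead of choosing.** Keeping all seven as routes to success with Bonferroni means 0.05 / 7 = 0.0071 per test. That needs about 102 per group, or leaves about 56% power at 64.

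**The case against.** The strongest reply is that the plan never says any significant result wins. Its one linking sentence speaks of corroboration between two methods. Read as requiring a significant mean-score test with some support from the periods, it implies almost no inflation and almost no loss of power, as shown above. A valid, adequately powered test is also already present. Both points stand: the defect is an unstated decision rule, and an inflated error rate has not been shown to be built in. The reply does not remove the defect, because the sentence is not a rule. It does not say which periods must agree, and it is silent on disagreement.

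Four stronger readings are tempting, and the documents do not support them.

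- **The false-positive rate is three to five times nominal.** That needs both an any-test-wins rule and correlations of 0.3 to 0.7. At 0.9 it is about double (11 / 5 = 2.2, or 9 / 5 = 1.8 with averaged scores).
- **Planned power collapses because all seven tests must agree.** No such rule appears. The resulting power would run from 4% to 63% over the same correlations, so no single figure represents it.
- **Half the pain scores go unused in the Wilcoxon tests.** A 12-hour period contains two 6-hourly scores and the text may intend both. All recorded scores enter the patient average in any case.
- **The 12-hour wording is a slip for 6-hour.** Twelve hours is also the grid for knee flexion and satisfaction. Changing it would double the time-specific tests and, under an any-test rule, raise the error to between 23% and 40% at correlations of 0.7 to 0.3.

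**Conclusion.** The point holds as a missing decision rule for the hypothesis that drives the sample size. If any significant result may be claimed, the false-positive chance at the final analysis is about 9% to 25%. That range rests on the assumed correlation of 0.9 to 0.3 and on how a 12-hour period is formed. With the interim look at the same unadjusted tests it is about 21% to 42%, counting any significant interim result; the plan's stopping text also asks for clear superiority, so these are upper figures for that rule. The freedom to alter tests adds an amount that cannot be calculated.

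A reader might infer that the trial has no controlled primary test, or that 64 per group is wrong. Neither follows. The mean-score comparison controls its error at 5% and has about 80% power at that size. The plan only fails to say that this comparison decides H1.a. The gap should be closed before outcome data are examined by arm.

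**What to change.** In VI.B:

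- Name one primary analysis for H1.a: the between-arm difference in each patient's mean 72-hour pain score, by two-sample t-test at two-sided 0.05, with a 95% confidence interval in pain points. This is the comparison behind 64 per group.
- Make a Wilcoxon test on the patient mean a sensitivity analysis, so that the parametric and rank methods address the same quantity.
- Make the 12-hour-period Wilcoxon comparisons descriptive or Holm-adjusted, and state how the two 6-hourly scores in each period are used.
- Limit the sentence on altering tests: changes only if documented before outcome data are seen by arm.

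The interim look should refer to the same named analysis. How alpha is shared between the interim and final looks is a separate matter that this change does not settle.

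The cost is the rewording of one paragraph and one sentence. The change needs no new data or patients and keeps the planned power. What is given up is the option to present an isolated time-point p-value as confirmation of H1.a.
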